5.11.1. Analysis of Anti-evinacumab Antibody (ADA) Variables

The ADA variables described in Section 4.11 will be summarized using descriptive statistics by patient group for the study in the ADA analysis set. Listings of ADA positivity and titers

presented by patient, time point, and study treatment received will be provided. Incidence of treatment-emergent and treatment-boosted ADA will be assessed as absolute occurrence (N) and percent of patients (%), summarized by patient group. The baseline ADA status in the parent study will be considered as the baseline ADA status of the patient.

Anti-drug antibody status and titer over the study duration may be classified as follows:

- Pre-existing immunoreactivity, defined as a positive ADA assay response at baseline, with all post-first dose ADA results negative, or a positive assay response at baseline, with all post-first dose ADA assay responses less than 9-fold over baseline titer levels.
- Treatment emergent - defined as any post- first dose ADA positive response when baseline results are negative or missing.
 - Persistent - A positive result in the ADA assay detected in at least 2 consecutive post-first dose samples separated by at least a 16-week [based on nominal sampling time], with no ADA-negative results in-between, regardless of any missing samples
 - Indeterminate - A positive result in the ADA assay at the last collected and analyzed time point
 - Transient - Not persistent or indeterminate
- Treatment boosted - defined as any post- first dose ADA response that is at least 9-fold over baseline titer levels when baseline results are positive

Samples positive in the ADA assay will be further characterized for ADA titers and for the presence of neutralizing antibody (NAb) response.

- Titer category for subjects, by maximum ADA titer value:
 - Low (titer <1,000)
 - Moderate ($1,000 \leq \text{titer} \leq 10,000$)
 - High (titer >10,000)
- NAb status (positive or negative)

NAb status (positive or negative) will be reported in the NAb analysis set. The impact of NAb on concentrations of evinacumab, safety and efficacy will be evaluated.

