4.4. Anti-Drug Antibody Variables

Anti-drug antibody (ADA) variables include status (positive or negative) and titer as follows:

- Treatment emergent ADA response, defined as any post-dose positive ADA assay response when the baseline results are negative or missing.
- Treatment boosted ADA response, defined as any post-dose positive ADA assay response that is 9-fold or greater over baseline titer levels when baseline is positive in the ADA assay

The definition of persistent and transient ADA will be defined a priori in the SAP.

- Titer values
- Titer category, by patient's maximal titer value
 - Low (titer <1,000)
 - Moderate ($1,000 \leq \text{titer} \leq 10,000$)
 - High (titer >10,000)
- Neutralizing ADA for samples that are positive in the ADA assay

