5.11.2. Association of Immunogenicity with Exposure, Safety and Efficacy

Associations between ADA response and titer categories and systemic exposure to evinacumab may be explored. Plots of evinacumab concentration may be provided for analyzing the potential impact of titer (high, moderate or low), treatment-emergent, persistent ADA and NAb responses on drug exposure.

Associations between the ADA response and safety events may be explored.

Associations between the ADA variables and key efficacy endpoints may be explored for the evinacumab treated group. Plots of efficacy variables may be analyzed for potential impact of treatment-emergent ADA on efficacy.

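### SAP 5.11.1: the persistent and indeterminate ADA sub-classes overlap as written, so the three sub-classes can sum to more than the treatment-emergent total (minor)

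*SAP*

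**What the plan says.** Protocol 4.4 defers the detail to the SAP: "The definition of persistent and transient ADA will be defined a priori in the SAP". SAP 5.11.1 supplies it, introduced in permissive terms: "Anti-drug antibody status and titer over the study duration may be classified as follows".

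The parent class is treatment-emergent ADA, "defined as any post- first dose ADA positive response when baseline results are negative or missing". It has three sub-classes:

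- **Persistent:** "A positive result in the ADA assay detected in at least 2 consecutive post-first dose samples separated by at least a 16-week" interval on nominal sampling times, with no negative result in between.
- **Indeterminate:** "A positive result in the ADA assay at the last collected and analyzed time point".
- **Transient:** "Not persistent or indeterminate".

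The results that the section commits to giving as counts and percentages are at the parent level: "Incidence of treatment-emergent and treatment-boosted ADA will be assessed as absolute occurrence (N) and percent of patients (%), summarized by patient group".

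**The concern.** Transient is written as whatever is left after the other two classes, which signals that a three-way split is intended. The wording does not deliver one. Indeterminate depends only on the last analysed sample, persistent depends on any qualifying pair of samples, and nothing stops one patient from satisfying both.

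The patients concerned are those whose ADA lasts and is still present at the end of sampling. Read literally, they also enter the indeterminate count, although their persistence has already been established. That class then mixes patients of unknown duration with patients of demonstrated duration, and the sub-class counts need not add up to the treatment-emergent count. ADA development is a secondary objective (Protocol 2.2, SAP 1.2.2), so the rule should give one answer per patient.

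**Working it through.** The documents give no figure for this point, so there is nothing to reproduce. The check is whether the planned sampling times allow both definitions to be met, and how often.

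**Inputs**

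- ADA samples are planned at baseline, week 24, each visit F, EOT and EOS (Protocol Table 3).
- Visits A to F follow week 24 at 4-week intervals and then repeat (Protocol 8.1.3, footnote 13), so visit F comes every 6 × 4 = 24 weeks: week 48, week 72 and so on.
- EOT is 4 weeks after the last dose (footnote 14). EOS is 24 weeks after the last dose (Table 3). The gap is 24 − 4 = 20 weeks.
- Patients who continue treatment outside the trial may skip follow-up, and EOT is then their last sample (footnote 14).

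**Gaps against the 16-week rule**

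- Week 24 to visit F, or one visit F to the next: 24 weeks, which qualifies.
- EOT to EOS: 20 weeks, which qualifies.
- Last visit F to EOT: 4, 8, 12, 16, 20 or 24 weeks when the last dose is at visit F, A, B, C, D or E respectively. The gap qualifies at 16 weeks or more, but not at 4, 8 or 12.

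Two ordinary courses therefore meet both definitions: positive at both EOT and EOS, and positive at week 24 and visit F and still positive at the last sample.

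**Enumeration**

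Take every pattern with at least one positive post-dose result, baseline negative or missing, and apply the definitions literally. With n samples there are 2^n − 1 patterns: 15 for n = 4 and 7 for n = 3.

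| Sample weeks | Patterns | Persistent | Indeterminate | Both | Transient | Literal sum |
|---|---|---|---|---|---|---|
| 24, 48, 52, 72 (follow-up done) | 15 | 7 | 8 | 5 | 5 | 7 + 8 + 5 = 20 |
| 24, 48, 64, 84 (follow-up done) | 15 | 8 | 8 | 5 | 4 | 8 + 8 + 4 = 20 |
| 24, 48, 52 (no follow-up) | 7 | 2 | 4 | 1 | 2 | 2 + 4 + 2 = 8 |
| 24, 48, 64 (no follow-up) | 7 | 3 | 4 | 2 | 2 | 3 + 4 + 2 = 9 |

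In each row the excess over the number of patterns equals the number meeting both definitions: 20 − 15 = 5, 20 − 15 = 5, 8 − 7 = 1 and 9 − 7 = 2. The counts are the same whether the 16 weeks is read as the gap between adjacent samples or as the span of an unbroken positive run.

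**With the overlap removed from indeterminate**

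- 24, 48, 52, 72: 7 + (8 − 5) + 5 = 15
- 24, 48, 64, 84: 8 + (8 − 5) + 4 = 15
- 24, 48, 52: 2 + (4 − 1) + 2 = 7
- 24, 48, 64: 3 + (4 − 2) + 2 = 7

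Each sum equals the number of patterns. Persistent and transient do not move.

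**The case against.** The strongest reply is that the text can be read sensibly as it stands. The classes are listed in the order persistent, indeterminate, transient, and a patient already shown to be persistent is not indeterminate in any ordinary sense. A programmer may well assign persistent first. The SAP nowhere says that a patient is counted twice. This is fair, and it is why the point is minor. But the order is never stated as a rule, and the literal definition of indeterminate includes persistent patients.

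A reader might also infer more than the documents support:

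- **That two positives at the end of sampling always put a patient in both classes.** They do not. The samples must be at least 16 nominal weeks apart. Without follow-up, a patient positive only at the last visit F and at EOT, with a gap of 4, 8 or 12 weeks, is indeterminate only. The sub-classes also apply only when baseline ADA is negative or missing.
- **That the ADA results as a whole are wrong.** Treatment-emergent and treatment-boosted incidence, titer category and neutralizing-antibody status do not use the sub-classes. Transient is the complement of the other two, so it is the same however the overlap is resolved.
- **That the concentration plots in SAP 5.11.2 are compromised.** These may examine "treatment-emergent, persistent ADA and NAb responses on drug exposure", but persistent has its own self-contained definition and its membership does not depend on how indeterminate is worded. It would change only if a programmer gave indeterminate precedence. On weeks 24, 48, 52 and 72, persistent would then hold 7 − 5 = 2 patterns instead of 7. The SAP does not tell anyone to do that, and the plots are optional.
- **That Protocol 4.4 is breached.** It asks the SAP to define persistent and transient, and the SAP defines both.

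**Conclusion.** Wrong as written, minor. The persistent and indeterminate definitions in SAP 5.11.1 are not mutually exclusive, and no precedence is stated. Read literally, the indeterminate count includes persistent patients who are positive at their last analysed sample, and the three sub-classes can exceed the treatment-emergent total.

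In the schedules tabulated, 5 of 15 positive patterns meet both definitions when follow-up is completed, and 1 or 2 of 7 when EOT is the last sample. This assumes nominal sampling times, no missing samples, and a last dose between week 48 and week 68; longer treatment adds further visit F samples and was not enumerated. The patterns are not equally likely, and the documents give no expected number of ADA-positive patients, so these counts show that the overlap is ordinary but do not predict its size in the trial.

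The effect is confined to the indeterminate label in an optional, descriptive classification. No safety or lipid endpoint is touched.

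**What to change.** In SAP 5.11.1, define indeterminate as positive at the last collected and analysed time point and not meeting the persistent definition. State that the classes are assigned in the order persistent, then indeterminate, then transient.

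This makes the three classes an exact partition of treatment-emergent ADA. It leaves the treatment-emergent total, the persistent definition and the transient count as they are. The cost is one clause. It needs no new data or sampling, and SAP section 1 allows the plan to be revised before database lock.

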5.11.2. Association of Immunogenicity with Exposure, Safety and Efficacy

Associations between ADA response and titer categories and systemic exposure to evinacumab may be explored. Plots of evinacumab concentration may be provided for analyzing the potential impact of titer (high, moderate or low), treatment-emergent, persistent ADA and NAb responses on drug exposure.

Associations between the ADA response and safety events may be explored.

Associations between the ADA variables and key efficacy endpoints may be explored for the evinacumab treated group. Plots of efficacy variables may be analyzed for potential impact of treatment-emergent ADA on efficacy.

6. DATA CONVENTIONS

The following analysis conventions will be used in the statistical analysis.

6.1. Definition of Baseline for Efficacy/Safety Variables

Unless otherwise specified, the baseline value used for determining percent and absolute change for each patient is defined as follows:

- For patients who participated in previous evinacumab study R1500-CL-1629, baseline is defined as the last obtained value before the first dose of double-blind study drug in R1500-CL-1629
- For patients who participated in previous evinacumab study R1500-CL-1331 or did not participate in any previous evinacumab study, baseline is defined as the last obtained value before the first dose of study drug in R1500-CL-1719 (Note: Baseline for patients who participated in R1500-CL-1331 is defined as the baseline from the R1500-CL-1719 study due to the long time between the last study treatment in R1500-CL-1331 and the first study treatment in R1500-CL-1719).

6.2. Data Handling Convention for Efficacy Variables

Missing data of efficacy variables will not be imputed for the efficacy data summary analyses.

6.3. Data Handling Convention for Missing Data

Missing data will not be imputed in listings. This section includes the methods for missing data imputation for some summary analyses, if necessary.

Date of First/Last Study Treatment

Since the study drug is administered at the site, the date of study drug administration is filled in e-CRF. No missing data is expected. Date of first/last administration is the first/last start date of study drug filled in e-CRF.

Adverse Event

If the intensity of a TEAE is missing, it will be classified as “severe” in the frequency tables by intensity of TEAEs. If the assessment of relationship of a TEAE to the investigational product is missing, it will be classified as related to the investigational product.

When the partial AE date information does not indicate that the AE started prior to study treatment or after the TEAE period, the AE will be classified as treatment-emergent.

Medication/Procedure

No imputation of medication/procedure start/end dates will be performed. If a medication date is missing or partially missing and it cannot be determined whether it was taken prior or

concomitantly or stopped prior to the first study treatment administration, it will be considered as concomitant medication/procedure.

Potentially Clinically Significant Value (PCSV)

If a patient has a missing baseline value, this patient will be grouped in the category “normal/missing at baseline.”

For PCSVs with 2 conditions, one based on a change from baseline value and the other on a threshold value or a normal range, with the first condition being missing, the PCSV will be based only on the second condition.

For a PCSV defined on a threshold and/or a normal range, this PCSV will be derived using this threshold if the normal range is missing; e.g., for eosinophils the PCSV is >0.5 giga/L or $>ULN$ if $ULN \geq 0.5$ giga/L. When ULN is missing, the value 0.5 should be used.

Measurements flagged as invalid by the laboratory will not be summarized or taken into account in the computation of PCSVs.

6.4. Visit Windows

Visit windows will be programmatically imposed on those efficacy and safety measures repeatedly collected over the course of the study. These visit windows are derived from the number of days in study, specifically assigning day ranges to represent the study assessment schedule provided in the protocol. Data analyzed by time point (including efficacy, laboratory safety data, vital signs, ECG, quality of life, drug concentration and ADA) will be summarized using the analysis windows given in Appendix 10.2. These analysis windows will be applicable for all analyses, and they are defined to provide more homogeneous data for time point-specific analyses. If multiple valid values of a variable exist within an analysis window, the nearest from the targeted study day will be selected for analysis, unless otherwise specified. If the difference is a tie, the value after the targeted study day will be used. If multiple valid values of a variable exist within a same day, then the first value of the day will be selected when time is available, else the scheduled visit will be selected.

6.5. Unscheduled Assessments

For efficacy, safety laboratory data, vital signs, ECG, unscheduled visit measurements may be used to provide a measurement for a time point, including baseline, if appropriate according to their definitions. The measurements may also be used to determine abnormal values, AESIs, and PCSVs.

6.6. Pooling of Centers for Statistical Analyses

Not applicable.

6.7. Statistical Technical Issues

Not applicable.

7. TIMING OF STATISTICAL ANALYSES

In order to provide information from this study, data may be analyzed on an ongoing basis. The results will not be used to change the conduct of the ongoing study in any aspect.

Additionally, an interim analysis is planned for the subpopulation of adolescent patients. This planned interim analysis will be conducted as soon as all adolescent patients have been enrolled and all their data through week 24 has been collected and validated. For adolescent patients, the analysis will consist of the final analysis of the primary (safety) and secondary (lipids) endpoints collected during the initial 24 weeks of study treatment exposure. The safety and lipids analyses will be performed on all data collected and validated at the time of this adolescent subpopulation interim analysis.

If the study is terminated prematurely, only those parameters required for the development program and/or reporting to regulatory authorities will be summarized.

8. SOFTWARE

All analyses will be done using SAS Version 9.4 or higher.

10. APPENDIX

10.1. Summary of Statistical Analyses

All safety and efficacy data will be summarized descriptively.

10.2. Windows for Analysis Time Points

Below are the definitions for the visit windows programmatically imposed on measures repeatedly collected over the course of the study. These visit windows reflect the study schedule of assessments as described in the protocol.

The visit windows are constructed using ranges applied to the number of days in study (study days) when the measure is collected. Below are the relevant definitions for the analysis visit windows:

1. Study day is defined as the number of days since the first study treatment administration +1. The first study treatment occurs on
2. Study Day 1.
3. Open-label study day is defined as the number of days since the first open-label study treatment administration+1
4. Since the protocol specifies that measurements be collected before study treatment is administered on a given day, it is appropriate that baseline include Day 1.
5. For enrolled but not treated patients, Day 1 is the day of enrollment.

Table 1: Global Analysis Windows

Visit label	Targeted Study Day	Analysis Window in Study Day
Screening	< Day 1	Measurement obtained prior to first study treatment, and not defined as baseline visit
Day 1	1	Measurement obtained closest to first study treatment, while remaining prior to first study treatment
Week 4	29	15 to 42
Week 4K, where K=2,3,...	28K+1	15+28*(K-1) to 42+28*(K-1)
FU – W4	last study trt to 28 days after last study trt	Last study trt to 56 days after last study trt
FU – W12	last study trt to 84 days after last study trt	57 days after last study trt to 112 days after last study trt
FU – W24	last study trt to 168 days after last study trt	113 days after last study trt to 196 days after last study trt
FU > W24	N/A	>196 days after last study trt
Study days are calculated from the day of first study treatment administration, the day of first study treatment administration being Day 1.		

10.3. List of AESIs with Data Sources and Definitions of SMQ/CMQ

Table 2: Summary of AESIs and the Methods of Data Collections and Derivations

AESI	Using an e-CRF specific tick box on AE page	Using Standard MedDRA Query (SMQ)/company MedDRA Query (CMQ) or lab data
Anaphylactic reactions	Yes	No
General allergic events	No	SMQ “hypersensitivity” (broad and narrow) excluding the following preferred terms linked to local injection site reactions (“infusion site dermatitis”, “infusion site hypersensitivity”, “infusion site rash”, “infusion site urticaria”, “injection site dermatitis”, “injection site hypersensitivity”, “injection site rash”, “injection site urticaria”, “injection site vasculitis”) plus “idiopathic angioedema”
Infusion reactions	Yes	No
Hepatic Disorders	No	
 • SMQ Drug-related hepatic disorder • Potentially clinically significant value (PCSV) in Appendix 10.4 • Hy’s law eDISH plot
Pregnancy	Yes	No
Symptomatic overdose with investigational medicinal product	Yes	No
Neurocognitive events	Yes	
 • CMQ for neurocognitive events as defined based on Regulatory Agency request for another lipid lowering program (See Table 3 in Appendix 10.3 for the list of terms)
Neurologic events	Yes	No

AESI	Using an e-CRF specific tick box on AE page	Using Standard MedDRA Query (SMQ)/company MedDRA Query (CMQ) or lab data
New onset of diabetes (NOD) for patients without diabetes mellitus at baseline	No	
No medical history of diabetes as specified in Cardiovascular History and Cardiovascular Risk Factors and Medical History CRF pages, AND Hb1Ac < 6.5% at baseline
 
AND one of the following:
 
Lab criteria: At least 2 values of HbA1c \geq6.5% during the TEAE period. NOTE: For patients with only a single measurement available during the TEAE period, a single value \geq6.5% will be considered and qualify the patient as NOD by default. For patients with several HbA1c measurements but only with the last one \geq6.5%, this single value \geq6.5% will be considered and qualify the patient as NOD by default.
 
OR
 
Lab criteria: At least 2 values of fasting glucose \geq126 mg/dL (7.0 mmol/L). NOTE: For patients with only a single measurement available during the TEAE period, a single value \geq126 mg/dL (7.0 mmol/L) will NOT be considered and will NOT qualify the patient as NOD. For patients with several fasting glucose measurements but only with the last one \geq126 mg/dL (7.0 mmol/L), this single value \geq 126 mg/dL (7.0 mmol/L) will NOT be considered and will NOT qualify the patient as NOD.
 
OR
 
HLT Diabetes mellitus (including subtypes)
 
OR
 
- Initiation of any new concomitant medication for hyperglycemia during the treatment period

Diabetic complication for patients with diabetes mellitus at baseline	No	For patients with medical history of diabetes as specified in Cardiovascular History and Cardiovascular Risk Factors and Medical History CRF pages, each of the following criteria will be considered, respectively:

AESI	Using an e-CRF specific tick box on AE page	Using Standard MedDRA Query (SMQ)/company MedDRA Query (CMQ) or lab data
		
 • Diabetes mellitus or diabetic complication TEAEs using HLTG Diabetic complications, HLT Diabetes mellitus (incl subtypes), and PTs Blood glucose increases, Glycosylated haemoglobin increased, Hyperglycaemia, Hyperglycaemic unconsciousness, and Hyperglycaemic seizure • Changes in diabetic medication dosage (specifically increases in dosage) or initiation of additional diabetic medication
Pancreatitis	Yes	No
Cataracts	No	HLT Cataract conditions
Immune complex diseases	No	SMQ (Narrow) Systemic lupus erythematosus SMQ (Narrow) Vasculitis SMQ (Narrow) Guillain-Barre syndrome
Muscle events/CK elevation	No	
 • Lab data analyses (e.g. PCSV) • All preferred terms under system organ class (SOC): Musculoskeletal and connective tissue disorders • Rhabdomyolysis/myopathy (Narrow SMQ)

Table 3: CMQ “Neurocognitive disorders – FDA’s recommendation”

MedDRA level	MedDRA Term Label
PTCD	Amnesia
PTCD	Amnesic disorder
PTCD	Anterograde Amnesia
PTCD	Behavioural and Psychiatric Symptoms of Dementia
PTCD	Change in sustained attention
LLTCD	Cognitive Deterioration
PTCD	Cognitive Disorder
LLTCD	Confusion
LLTCD	Confusion Aggravated
PTCD	Confusional State
PTCD	Delirium
PTCD	Dementia
PTCD	Dementia Alzheimer's type
LLTCD	Dementia Nos
LLTCD	Dementia Nos Aggravated
LLTCD	Dementia of the Alzheimer's type NOS
PTCD	Dementia with Lewy Bodies
PTCD	Disorientation
PTCD	Disturbance in attention
PTCD	Executive dysfunction
PTCD	Frontotemporal Dementia
LLTCD	Global Amnesia
PTCD	Illogical Thinking
PTCD	Impaired reasoning
PTCD	Incoherent
PTCD	Judgement impaired
PTCD	Memory Impairment
PTCD	Mental Impairment
LLTCD	Mental Impairment Nos
LLTCD	Mental State Abnormal Aggravated
PTCD	Mental Status Changes
PTCD	Mini Mental Status Examination Abnormal
PTCD	Presenile Dementia
PTCD	Retrograde Amnesia
PTCD	Senile Dementia
LLTCD	Senile Dementia Nos
LLTCD	Short-term Memory Loss
PTCD	Thinking Abnormal
LLTCD	Thinking Slowed
PTCD	Transient Global Amnesia
PTCD	Vascular Dementia

